STUDY PROTOCOL AND STATISTICAL ANALYSIS PLAN

Study title: A Randomized Controlled Trial to Investigate the Cognitive, Mood, Anti-inflammatory and Metabolic Effects of Chronic Oyster Mushroom Intervention in Older Adults.

Acronym: OYSCOG

Date: 01 October 2023

The Pleurotus oyster species is a common edible mushroom rich in ergothioneine, a bioactive compound with known neurocognitive benefits. The aim of the OYSCOG is to investigate the chronic effect (12-weeks) of the equivalent 1 portion of ergothioneine-rich Pleurotus oyster mushrooms (in dried powdered form) on cognition and mood, with examination of the potential inflammatory, metabolic, and neurological related mechanisms that may underlie these effects.

1. Sample Size Calculation

A power calculation based on similar research investigating the chronic benefits of other mushroom interventions on cognitive function suggests that 72 participants should give sufficient statistical power (with $\alpha=0.05$, $\beta=0.80$, Cohen's $d=0.60$). This calculation was based on the average Cohen's d value obtained from 7 RCTs examining the effect of Lion's Mane (Mori et al., 2009; Saitsu et al., 2019; Li et al., 2020; Grozier et al., 2022), Reishi mushroom (Tsuk et al., 2017; Wang et al., 2018) or vitamin D enriched mushroom (Zajak et al., 2020) on global cognitive performance.

To allow for a 10% attrition rate, 80 healthy older adults aged 60-80 years old will be recruited primarily from the University of Reading Ageing Research Panel and the local community. Given the parallel design of the RCT, the cohort will be half split to receive either the control intervention ($N=40$) or the oyster mushroom intervention ($N=40$).

2. Recruitment and Screening

Participants will be initially recruited using opportunity sampling. The study will be advertised via email and posters will be placed around public areas (eg university area, sports hall, library, churches, parkruns, GP practices). Furthermore, participants will be recruited from the Age UK Berkshire and the local community.

Before interested participants are enrolled in our study, they will be invited to attend a familiarisation session to our unit, to determine if they meet the eligibility criteria and they will be given an opportunity to become familiar with the cognitive task battery to reduce the influence of practice effects. Participants will be compensated with £100 for completing all study visits.

3. Inclusion/Exclusion criteria

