Inclusion criteria

- Aged between 60-80 years old
- Have normal vision and hearing
- Have healthy status
- Have normal body mass index (cutoff: $BMI \leq 30$)

Exclusion criteria

- Smokers
- Vegans/vegetarians
- Being diagnosed with psychiatric/neurological condition (eg., stroke, schizophrenia, depression, cognitive impairment, dementia)
- Being diagnosed with a learning/behavioural disorder (eg., dyslexia, autism, ADHD)
- Being diagnosed with a metabolic disease (eg., type I/II diabetes and cardiovascular disease), or suffer from unmedicated hypertension or thrombosis related disorders

- Being anaemic
- Taking disease medication such as anticoagulants, antiplatelet medication, dementia medication, antidepressants, antiepileptic medication, or thyroid medication
- Currently taking regular vitamin supplements (including prebiotics/probiotics)
- Have food allergies
- Having a difficulty in completing computer-based cognitive tasks

4. Randomisation Process

The study will be double blinded since neither the participants nor the researcher will know which intervention meal participants are receiving until the study is over. To achieve this, the Latin Square design will be followed, by using blocked randomisation with random permuted blocks of two. Another individual not being involved in this study, will assign a code to the placebo and mushroom intervention and these will be kept in a sealed envelope, concealed to the researcher enrolling and assessing participants.

5. OYSCOG study Protocol

During this 2-arm parallel double-blind study, participants will attend the University of Reading, Psychology department on three separate occasions; a) a familiarisation visit; b) a baseline visit, a week after the familiarisation visit and c) a post-visit, 12-weeks after the baseline visit.

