In the pre-screening phase, the participants interested in our study will be sent a link to REDCap containing online versions of a Health and Lifestyle Questionnaire and the Epic Norfolk Food Frequency Questionnaire (FFQ). Then, participants, will be contacted to attend a 3-hour familiarisation session at our department, during which the participant's weight, height and blood pressure will be checked, along with a finger-prick, to ensure that the participants are not anaemic. Furthermore, participants will complete the Raven's Progressive Matrices (RPM) measure of fluid intelligence and will perform the cognitive battery tasks twice to control for practice effects in the run up to the test session days. Also, the head and cap size measurements will be taken in a subset of participants (N=20 from each experimental group) that agreed to undertake the EEG at the testing visits.

At the end of the familiarisation visit, participants will be allocated to one of the treatment groups and they will receive a 12-week supply of the intervention powder in sachets. After the familiarisation visit, participants will be asked to follow a low flavonoid diet for 24-hours in advance of the two testing days. In both the baseline and post-visit testing sessions, participants will be instructed to perform several cognitive and mood related tasks. In addition to the behavioural tests, blood pressure, heart rate and body weight will be measured, and electroencephalogram (EEG) measurements will be recorded in a subset of participants using electrodes placed on the scalp for detecting electrical brain activity. Finally at the end of each testing visit, a blood sample will be taken. Each test visit will last approximately 2 hours. **Figure 1** summarises the OYSCOG testing protocol.

[figure not shown]

Figure 1: Study design of the parallel 2-arm OYSCOG RCT, investigating the chronic effects of ergothioneine-rich Pleurotus mushrooms on cognition, cognition, inflammation, and metabolism.

The cognitive-mood battery used will contain the following tasks:

- Positive and Negative Affect Schedule (PANAS-X)- In this mood task, participants are asked to rate their emotion on a 5-point Likert scale, in response to negative emotions (e.g., guilt, fear), positive emotions (e.g., attentiveness, joy) and other affect states (e.g., surprise, shyness).

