- Depression, Anxiety and Stress Scale - 21 items (DASS-21)- This 21-item measure assesses symptoms of depression, anxiety and stress. Each item is scored from 0-3 where higher scores indicate higher levels of distress in anxiety (scores range from 0 to >20), depression (0 to >28) or stress (0 to >34).
- Rey Auditory Verbal Learning Task (RAVLT)- This episodic memory task consists of 5 consecutive free recalls of the same 15 nouns presented as an auditory list (list A), followed by recall of a further 15 nouns presented as an interference list (list B) which is recalled only once. List A is subsequently recalled straight after list B and then again after a longer delay of around 30 minutes.
- Task Switching Task (TST) - In this executive function task, participants view 8 spaced radii of a circle above and below a bold line and a stimulus digit selected from 1-9 (except 5) appears clockwise in each segment, either above or below the bold line. Depending on the stimulus position in the segments, participants perform different tasks with each being switched every 4 trials.
- Corsi block tapping task (CBTT)- In this spatial working memory task, participants are shown 9 arranged blocks positioned on a computer screen and are asked to reproduce a given sequence by clicking on the blocks (using the mouse) in the same sequence as they see them.
- Simple and complex finger tapping task (SFT & CFT)- In this psychomotor function task, participants tap on a key as quickly as possible with the index finger of their dominant hand for 1 minute. They then tap out a specific sequence using 4 fingers, again for 1 minute.
- RAVLT word recognition- In this delayed memory task, participants are shown a sequential list of 50 nouns containing the words from lists A and B from the previously

described RAVLT task plus 20 additional words not previously heard, and are asked to indicate those from list A.

•N-back- In this working memory and attention task, participants are shown a series of stimuli, and they will have to respond to indicate whether the stimuli match the target presented at the beginning of the task. This task will be performed while also taking EEG measurements (using Brain Products software and 16 active electrodes), to examine changes in brain activity.

• Subjective mental fatigue- At the end of the cognitive battery participants are asked to rate their mental fatigue level on a 9-point Likert scale.

6. Statistical Plan

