All statistical analyses will be performed by using SPSS software. Initially, extreme outliers will be identified and excluded using boxplots (using 3*IQR rule), and subjects with missing data will be excluded from analysis. The main analysis will use a mixed ANOVA to investigate a) the main effect of time (within subject factor, baseline vs 12-weeks), b) the main effect of intervention (between subject factor, placebo vs oyster mushroom group) and c) the intervention*time interaction. For the outcome measures that show significant changes at baseline, a 1-way ANOVA will be applied by treating the baseline scores as a covariate to examine the main effect of intervention. In all analyses, a Bonferroni correction will be examined for post-hoc pairwise comparisons regardless of the significance of the overall F test statistic. Significant comparisons will be reported (*p<0.05, **p<0.01, ***p<0.001).

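### Section 6 deletes values beyond 3*IQR and drops incomplete subjects after allocation, does not say how the fences are drawn, and plans no analysis without these exclusions

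*Combined protocol and SAP*

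**What the plan says.** Section 6 (Statistical Plan) opens its analysis with this step: "Initially, extreme outliers will be identified and excluded using boxplots (using 3*IQR rule), and subjects with missing data will be excluded from analysis". A mixed ANOVA of baseline and 12-week scores by group follows.

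Section 5 fixes when the affected data arise: "At the end of the familiarisation visit, participants will be allocated to one of the treatment groups". The baseline visit comes a week later, so every baseline and 12-week value is collected after allocation.

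Four other statements bear on the point:

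- **Outcome scale.** Section 5 describes DASS-21 scores as running upwards from zero: "higher levels of distress in anxiety (scores range from 0 to >20), depression (0 to >28) or stress (0 to >34".
- **Population.** Section 3 excludes people "Being diagnosed with psychiatric/neurological condition (eg., stroke, schizophrenia, depression, cognitive impairment, dementia", and also people taking antidepressants.
- **Blinding.** Section 4 keeps the researcher blind until the study is over. A person outside the study "will assign a code to the placebo and mushroom intervention". Data cleaning is not mentioned.
- **Loss.** Section 1 provides for lost numbers only: "To allow for a 10% attrition rate, 80 healthy older adults".

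The plan does not say whether fences are pooled or drawn by arm, whether they are set before unblinding, or whether a missing value on one outcome removes the person from the others. It defines no analysis set and mentions no all-randomised analysis, imputation or sensitivity analysis.

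**The concern.** A boxplot rule removes a value because it is far out, not because it is wrong. If an outcome has a long right tail or piles up at zero, the values removed are real people with high scores. If the intervention lowers scores, more of those people are in the placebo arm, and removing them narrows the difference that the trial is meant to measure. On a mood scale given to people screened for diagnosed depression, those with symptoms are the ones who can improve.

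Dropping incomplete subjects is a second selection after allocation. It can bias the comparison if the reasons for dropping out differ between arms or depend on the outcome. The 10% allowance replaces numbers and does nothing about selection. As only the post-exclusion result is planned, a reader could not see what either step changed.

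**Working it through.** **The plan's own figure.** 72 / (1 - 0.10) = 80, as stated in Section 1. A full 10% loss leaves exactly 72, or 36 per arm, so there is no reserve for outlier deletions.

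**Fences.** A value is deleted if it lies below Q1 - 3*IQR or above Q3 + 3*IQR.

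- *Normal outcome.* Quartiles are at ±0.674 SD and the IQR is 1.349 SD, so the upper fence is 0.674 + 3 × 1.349 = 4.72 SD. With quartiles estimated from 72 people, about 57 values per million fall outside.
- *Pile-up at zero.* If 55 of 72 people score 0 (76.4%), both quartiles are 0, the IQR is 0 and both fences are 0. All 72 - 55 = 17 non-zero scores are deleted.

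**Simulated outlier deletion.** All distributions are assumptions, because the documents give none. Each setting has 20,000 trials. The test is a two-sample t-test on change, which is the intervention*time test. Fences are set at each visit, and a participant is removed if either visit is outside.

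Lognormal outcome, 36 per group, correlation 0.7 between visits, true 20% reduction with mushroom:

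| Log-SD | Removed, placebo / mushroom (pooled) | Effect kept | Power with / without deletion | Type I, pooled | Type I, per arm |
|---|---|---|---|---|---|
| 0.5 | 1.8% / 1.0% | 94% | 53.9% / 53.5% | 4.9% | 5.9% |
| 0.75 | 3.9% / 2.8% | 84% | 25.3% / 23.7% | 5.0% | 7.7% |
| 1.0 | 6.3% / 5.0% | 70% | 14.6% / 12.8% | 4.9% | 9.2% |

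Over correlations of 0.5-0.8, or reductions of 10-30%, the effect kept is 93-95%, 81-86% and 66-71% respectively.

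Zero-bounded count (gamma-Poisson, capped at 21), true 30% reduction:

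| At zero | Removed, placebo / mushroom (pooled) | Effect kept | Power with / without deletion | Type I, pooled | Type I, per arm |
|---|---|---|---|---|---|
| 20% | 2.2% / 1.1% | 94% | 40.2% / 43.0% | 4.8% | 5.9% |
| 33% | 2.1% / 1.1% | 90% | 22.2% / 24.2% | 4.9% | 6.3% |
| 50% | 3.4% / 2.1% | 82% | 12.9% / 14.5% | 5.0% | 7.9% |
| 58% | 6.0% / 4.4% | 67% | 11.3% / 14.1% | 5.0% | 9.2% |
| 71% | 13.7% / 11.4% | 57% | 6.9% / 9.5% | 4.7% | 22.5% |

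The cap is a modelling choice. In the first row (mean 4, shape 1) the uncapped score reaches 21 with probability 0.8^21 = 0.9%, so it matters little.

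**Dropout.** Assumptions: 40 per arm, correlation 0.7, higher scores better, placebo loses 10% at random. If the lowest 10% on some variable leave the mushroom arm only, the mean of that variable among those who stay rises by 0.195 SD. The bias in change, with no true effect, is that figure times the slope of change on the variable:

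- by baseline: 0.195 × (0.7 - 1) = -0.059 SD (simulated, lowest 4 of 40: -0.056)
- by week-12 score: 0.195 × (1 - 0.7) = 0.059 SD (simulated: 0.056)
- by change, whose SD is √(2 × 0.3) = 0.775: 0.195 × 0.775 = 0.151 SD (simulated: 0.147)

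A softer rule (log-odds of leaving up by 1 per SD lower, average 10%, mushroom only) gives -0.027, 0.027 and 0.070 SD. The same soft rule in both arms gives 0.00 with no true effect. With a true effect of 0.6 SD it gives 0.000, -0.010 and -0.031 SD.

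**The case against.** The strongest defence is that the rule is numerical, set in advance and uses the wide 3*IQR limit. In a computerised battery its usual purpose is to catch lapses and misunderstood instructions. That stands. For a normal outcome with a 0.46 SD effect, 36 per group, correlation 0.7 and 1% of values per visit displaced by 8 SD, pooled deletion gave 69% power against 39% without it. At 2% displaced it gave 67% against 25%. The estimate stayed at 0.46 and type I error was 5.2% (1% case). Taking the rule out of the main analysis would therefore be a trade-off, not a clear gain.

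It is also fair that the harm is conditional. The DASS-21 ranges say nothing about how many people score zero, and excluding diagnosed depression does not show that three quarters do. Dropout bias is small unless dropout is both selective and one-armed.

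The defence does not answer the missing parallel result or the silence on how fences are drawn. Blinding does not settle the second: with one code per intervention, boxplots by coded arm remain possible.

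**Conclusion.** The point holds as a cheap improvement. The exclusions after allocation, and the absence of any analysis without them, are plain from the text and need no assumption. Their size does. Under assumed skewness or pile-up at zero, pooled fences leave 57-95% of the raw-scale effect, with type I error of 4.7-5.0%. Dropout bias runs from about 0 to 0.03 SD in size under a common rule to about 0.15 SD in the extreme one-arm case.

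A reader might infer more than the documents support:

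- **That the false-positive rate is inflated.** This needs per-arm fences, which the plan leaves open but does not state. The 22.5% figure also needs 71% of scores at zero.
- **That every outcome is affected.** Near-normal outcomes are not.
- **That deletion costs much power.** In the lognormal cases power rises slightly; in the zero-bounded cases it falls by 1.6 to 2.8 points.
- **That complete-case analysis is biased here.** That depends on why people leave, which is unknown.
- **That everyone without EEG data would be dropped from all analyses.** EEG is planned only for those whose head and cap measurements "will be taken in a subset of participants (N=20 from each experimental group", that is 40 of 80. The missing-data rule does not say it works across outcomes, so this calls for clarification only.

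**What to change.** Add to Section 6, before unblinding:

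1. **Fences.** Compute them on both arms pooled, before unblinding, outcome by outcome. Do not apply the rule to an outcome whose pooled IQR is 0.
2. **Parallel analysis.** Also analyse every outcome with all recorded values kept, except those shown, blind to allocation, to be measurement, entry or task errors. Report both results, with numbers excluded per arm.
3. **Missing data by outcome.** A missing value on one outcome does not remove the participant from the others.
4. **One sensitivity analysis of all randomised participants, in their allocated group.** Impute missing 12-week values from arm and baseline, for example by multiple imputation, so that people allocated but without a baseline are included. Then shift the imputed mushroom values towards worse scores by stated amounts, such as 0.5, 1.0 and 1.5 SD. Report dropouts and reasons per arm.

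Item 1 does not protect an outcome just short of an IQR of 0; item 2 makes the effect of deletion visible there. Item 4 does not remove bias. It shows how much worse dropouts must be to change the conclusion: with 4 of 40 missing, each 0.5 SD moves the estimate by 0.5 × 4/40 = 0.05 SD.

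The 3*IQR rule and the mixed ANOVA can stay in the main analysis. Whether a baseline-adjusted model should replace the mixed ANOVA is a separate question. No extra participants or visits are needed. The cost is SAP wording, slightly more analysis and reporting, and two results per outcome that may differ.

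### Baseline adjustment depends on an undefined baseline significance test, and the mixed ANOVA does not say which term tests efficacy; ANCOVA should be pre-specified for outcomes measured at both visits

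*Combined protocol and SAP*

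**What the plan says.** Section 6 (Statistical Plan) makes a mixed ANOVA the main analysis. It lists the effect of time, then "b) the main effect of intervention (between subject factor, placebo vs oyster mushroom group"), then "c) the intervention*time interaction". None is given priority.

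The baseline score enters as a covariate only under a condition: "For the outcome measures that show significant changes at baseline, a 1-way ANOVA will be applied by treating the baseline scores as a covariate". That branch does name its term, the main effect of intervention. The plan does not define the condition: it speaks of change at a single visit and gives no contrast, test or threshold. It also does not say whether the mixed ANOVA is still reported for these outcomes.

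The section adds a Bonferroni correction for "post-hoc pairwise comparisons regardless of the significance of the overall F test statistic".

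Section 5 shows that baseline data will exist: "In both the baseline and post-visit testing sessions, participants will be instructed to perform several cognitive and mood related tasks". Blood pressure, heart rate, weight and a blood sample are also taken at both testing visits, and EEG in a subset. Allocation and sachet supply happen at the end of the familiarisation visit, a week before baseline. The documents do not say when intake starts.

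Section 1 states that "72 participants should give sufficient statistical power", with alpha 0.05 and d=0.60. It gives no baseline-to-12-week correlation and does not say which SD standardises d.

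**The concern.** Two analysts could follow Section 6 faithfully and report different tests for the same outcome. They could differ on what triggers adjustment, on whether the adjusted result supersedes the other, and on which mixed-ANOVA term they read. The label 'main effect of intervention' also covers two quantities: a baseline-adjusted 12-week difference in the conditional branch, and an average over both visits in the mixed ANOVA.

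The selection rule is also the wrong tool. Under randomisation a baseline test detects only chance. Whether adjustment helps depends on how strongly baseline predicts the 12-week score, which that test does not measure. At stake are precision that data already being collected could supply, and a fixed, single test of efficacy for each outcome.

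**Working it through.** **Inputs.** From Section 1: 72 evaluable (36 per group), alpha 0.05, d=0.60. From Section 6: the models. Assumed: r = 0.3, 0.5, 0.7, 0.8; equal SDs at both visits; bivariate normal scores; two-sided tests; the trigger is a between-group baseline t-test at p<0.05, with ANCOVA then replacing the mixed ANOVA; intake starts after the baseline visit.

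**The plan's own figure.** A two-sample t-test with d=0.60 and 80% power needs 36 per group (72) one-sided, or 45 per group (90) two-sided. With 36 per group, two-sided power is 70.9%. 72/0.9 = 80 reproduces the recruitment target. Sidedness is a separate matter; the comparisons below are all two-sided at the same n, so their gaps reflect only the choice of model.

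**Variance, in units of the 12-week variance.** The interaction in a 2x2 mixed ANOVA is the comparison of change scores, with factor 2(1-r). ANCOVA has factor 1-r². The ratio is 2(1-r)/(1-r²) = 2/(1+r), so the large-sample ratio of CI widths is √(2/(1+r)).

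| r | 2/(1+r) | CI ratio, large sample | CI ratio, simulated, 36 per group |
|---|---|---|---|
| 0.3 | 1.54 | 1.240 | 1.231 |
| 0.5 | 1.33 | 1.155 | 1.146 |
| 0.7 | 1.18 | 1.085 | 1.076 |
| 0.8 | 1.11 | 1.054 | 1.046 |

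**Power with d in 12-week SD units.** The standardised effect is 0.60/√(2(1-r)) for the interaction and 0.60/√(1-r²) for ANCOVA. At r=0.5 these are 0.60/1 = 0.600 and 0.60/√0.75 = 0.693. Simulation (200,000 trials per setting, 36 per group):

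| r | Interaction alone | Two-stage rule | ANCOVA |
|---|---|---|---|
| 0.3 | 56.2% | 57.2% | 74.2% |
| 0.5 | 71.0% | 71.9% | 82.2% |
| 0.7 | 90.0% | 90.5% | 93.7% |
| 0.8 | 97.8% | 97.9% | 98.6% |

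The rule recovers little of the gain because it seldom fires. A trigger at 0.01 or 0.10 moves its power by at most about 1 point.

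**Power with d in change-score SD units.** The interaction effect is 0.60 at every r, and the ANCOVA effect is 0.60·√(2/(1+r)). The two-stage rule has about 71-72% throughout; ANCOVA has 87, 82, 77 and 75%.

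**Intervention main effect in the mixed ANOVA.** Averaging the visits halves a 12-week effect, and the average has variance (1+r)/2, so the equivalent factor is 4(1+r)/2 = 2(1+r). Power is 34, 31, 28 and 26% (12-week SD units).

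**Type I error, rule with one test.** Rejection under the null is 4.1, 4.4, 4.7 and 4.8%. It falls below 5% because ANCOVA replaces the interaction where imbalance is greatest. At r=0.3 the interaction would reject in 24.3% of triggered cases and ANCOVA in about 5%, so 0.05 - 0.05×(0.243-0.05) = 0.040.

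**Type I error, either term counted.** With equal SDs the sum and difference of the two scores are uncorrelated, so the main effect and interaction tests are close to independent: 1-0.95² = 0.0975. Simulation gives 9.7-9.9% when the mixed ANOVA is read for every outcome, and 6-7% if ANCOVA replaces both terms where triggered. Adding the 12-week pairwise comparison with Bonferroni correction for two comparisons gives 9.7-10.1%, so it adds little.

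**Not covered.** Fatigue is a single item on which participants "rate their mental fatigue level on a 9-point Likert scale", so normality is doubtful. Outlier and missing-data exclusions may take n below 36. No power is given for the EEG subset ("N=20 from each experimental group"), because d=0.60 comes from trials of global cognition.

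**The case against.** The strongest reply is that the planned analysis is sound and the gain may be small. Much of this stands. The interaction is a valid test and is unbiased over randomisations. With r=0.8 and d in 12-week SD units, ANCOVA gains about 1 point of power. In change-score units the gap at r=0.8 is still about 4 points (71% against 75%), so a small gain is not assured. Participants perform the battery twice before baseline, but the documents report no r from which to judge.

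Four stronger readings are tempting, and the documents do not support them:

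- *The two-stage rule inflates false positives.* With one test per outcome it does not; rejection is 4-5%.
- *The plan has a 10% false-positive rate per outcome.* That needs either mixed-ANOVA term to count as success, and Section 6 does not say so. It leaves the choice open.
- *No efficacy term is named anywhere.* The conditional ANCOVA branch names one. The gap is in the mixed ANOVA and in how the two analyses relate.
- *Pairwise tests made regardless of the F test add serious inflation.* The same sentence applies a Bonferroni correction, which removes most of it.

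A further objection is that both the 5% chance trigger and ANCOVA need a baseline taken before intake, while sachets are supplied a week earlier. This stands as a premise to confirm. A 12-week supply and a 12-week interval suggest that intake starts at baseline, but no text says so. The planned interaction needs the same premise, so this does not favour the current rule.

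**Conclusion.** The concern holds in this form and should be acted on. The firm defects, at any r, are the undefined trigger, the unstated relation between the two analyses and the unranked mixed-ANOVA terms. The loss of precision is real, but its size is unknown. Against ANCOVA, the rule gives up about 17 points of power at r=0.3, 10 at r=0.5, 3 at r=0.7 and 1 at r=0.8 in 12-week SD units; in change-score SD units the loss is about 15, 10, 6 and 4 points. These figures assume normal scores, equal SDs, 36 per group, a two-sided 0.05 level, a between-group baseline trigger at 0.05 and a pre-intake baseline. The CI-width comparison does not depend on d or sidedness. A reader should not infer that the interaction is biased or that the planned rule is itself anti-conservative.

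**What to change.** Replace the conditional rule in Section 6 with:

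> For every outcome measured at both visits, the 12-week score is compared between groups by ANCOVA with the baseline score as covariate; the adjusted group difference with 95% CI is the test of efficacy. No significance test of baseline differences is used to choose the model.

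Keep the mixed ANOVA as supportive only. State that its intervention main effect and the post-hoc pairwise comparisons are not evidence of efficacy. Confirm in Section 5 that baseline is measured before the first intake.

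The cost is one paragraph in Section 6 and one confirming sentence in Section 5, both settled before unblinding. Baseline is already measured and a baseline-covariate analysis is already in the plan, so no extra participants, visits or data are needed.

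### Section 6 names no primary outcome and no deciding between-group test, corrects nothing across outcomes, and no outcome in the trial matches the one behind the sample size

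*Combined protocol and SAP*

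**What the plan says.** Section 6 (Statistical Plan) gives the main analysis as a mixed ANOVA with three effects: time, then "b) the main effect of intervention (between subject factor, placebo vs oyster mushroom group) and c) the intervention*time interaction". None is given priority.

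A second analysis is conditional: "For the outcome measures that show significant changes at baseline, a 1-way ANOVA will be applied by treating the baseline scores as a covariate". The section does not say whether this replaces the mixed ANOVA for those outcomes or is run as well.

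On multiplicity, the section says only that "a Bonferroni correction will be examined for post-hoc pairwise comparisons", whatever the overall F test shows. The pairs are not listed, and results are flagged from p<0.05.

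Section 1 (Sample Size Calculation) states that "72 participants should give sufficient statistical power", using d=0.60 averaged over seven trials of other mushroom products "on global cognitive performance".

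Section 5 (OYSCOG study Protocol) lists nine cognitive, mood and fatigue entries, several with more than one score. It adds EEG, blood, blood pressure, heart rate and weight. No section labels any outcome primary or secondary.

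**The concern.** Four gaps combine.

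1. With no primary outcome, nothing fixed in advance tells the reader which result decides the trial. The Bonferroni rule does not help: it works within an outcome, and because each factor has two levels, each main effect has a single pair and nothing to correct.
2. Two between-group terms are tested in the mixed ANOVA, and a third analysis applies to some outcomes depending on the data. They answer different questions. The intervention main effect averages baseline with week 12, so it dilutes an effect present only at week 12.
3. The effect size behind the sample size belongs to a global cognitive measure. Nothing in the battery or in Section 6 is defined as one, so no single test answers the question the trial was sized for.
4. Because the post-hoc pairs are not listed, the plan does not rule out a within-arm change being read as efficacy.

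At stake is the credibility of any positive finding. A primary outcome chosen after unblinding would not repair this.

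**Working it through.** **Inputs from the documents.** d=0.60, alpha 0.05, 72 evaluable (36 per arm), 10% attrition, 80 recruited (Section 1; the value 0.80 given for beta is read as power). Two arms and two visits (Sections 5 and 6).

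**Assumptions, because the documents give no figure.** Two-sided 0.05 per test. Equal correlation between scores of 0, 0.3, 0.5 or 0.7. Baseline to 12-week correlation r of 0.5, 0.6 or 0.7. The count of scores is mine: PANAS-X 2, DASS-21 3, RAVLT 1, task switching 1, Corsi 1, simple and complex finger tapping 2, RAVLT recognition 1, N-back 1, fatigue 1, total 13. One score per battery entry gives 9.

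**Step 1: the plan's own figure.** For a two-group t-test the noncentrality is d·√(n/2).
- One-sided: 35 per arm gives 79.96% and 36 per arm gives 81%. So 36 per arm, or 72, and 72/0.90 = 80. The plan's figures are reproduced.
- Two-sided: 36 per arm gives 71%, 44 gives 79.5% and 45 gives 80.4%. So 90 evaluable would be needed.

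**Step 2: chance of at least one false-positive interaction.** With k uncorrelated null scores this is 1 − 0.95^k: 1 − 0.95^13 = 0.487 and 1 − 0.95^9 = 0.370. With correlation ρ, and c = 1.96, it is 1 − ∫ φ(u)·[Φ((c − √ρ·u)/√(1−ρ)) − Φ((−c − √ρ·u)/√(1−ρ))]^k du.

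| Scores | ρ=0 | ρ=0.3 | ρ=0.5 | ρ=0.7 |
|---|---|---|---|---|
| 13 | 49% | 42% | 33% | 24% |
| 9 | 37% | 33% | 27% | 20% |

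Simulated trials with 36 per arm and 13 scores agree (48.5%, 42.1%, 33.3%, 24.3%).

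**Step 3: if other terms also count as evidence.** These are for 13 scores, 36 per arm and r=0.6. The baseline condition in Section 6 is read as a between-group difference at baseline with p<0.05, which is an interpretation. The first row at ρ=0 can be checked by hand: the two terms are independent under the null, so 1 − 0.95^26 = 0.736.

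| Evidence counted | ρ=0 | ρ=0.3 | ρ=0.5 | ρ=0.7 |
|---|---|---|---|---|
| Interaction or intervention main effect, ANOVA for all | 74% | 66% | 56% | 43% |
| Same, covariate analysis replacing ANOVA where baselines differ | 58% | 52% | 44% | 34% |
| Interaction, or covariate analysis where it replaces | 45% | 39% | 32% | 23% |

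Blood, EEG, blood pressure, heart rate and weight are not counted and would add to these.

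**Step 4: power by term.** The effect is d=0.60 at week 12 with equal baselines, 36 per arm. The standardised effect is 0.60/√(2(1−r)) for the interaction and 0.30/√((1+r)/2) for the intervention main effect.

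| r | Interaction effect | Power | Main effect | Power |
|---|---|---|---|---|
| 0.5 | 0.600 | 71% | 0.346 | 31% |
| 0.6 | 0.671 | 80% | 0.335 | 29% |
| 0.7 | 0.775 | 90% | 0.325 | 28% |

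**The case against.** The strongest reply is that the interaction is the conventional efficacy term in a pre-post mixed ANOVA, so the intent is clear. The plan does not say so, and its covariate branch uses a different term. Even if granted, this disposes only of the larger percentages in Step 3, which assume that a significant main effect would be claimed as efficacy. Step 2 concerns the interaction alone.

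The count of 13 is a choice and mixes domains: six of the scores are mood or fatigue. The seven cognitive scores alone give 1 − 0.95^7 = 30% at zero correlation. But the stated aim covers mood as well as cognition, and even 9 scores correlated at 0.7 give 20%, four times the nominal rate.

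Three further points stand as limits:
- Section 1 uses the global cognitive measure to describe the earlier trials and does not declare it as this trial's endpoint. What remains is that nothing here is linked to it.
- The covariate branch does not itself inflate error: 45% to 23%, against 49% to 24% for the interaction alone. The objection to it is ambiguity.
- The plan does not say that within-arm changes will be read as efficacy. That part is a request for clarification.

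The trial could be regarded as exploratory, but the document never says so, and it presents a power calculation for a cognitive effect.

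**Conclusion.** The concern holds and must be fixed before unblinding. That no primary outcome, deciding term or rule across outcomes is given follows from the text and needs no assumption. The same is true of the missing link between the sized effect and any tested outcome.

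The size of the false-positive risk is illustrative. For the interaction alone it runs from 20% (9 scores, correlation 0.7) to 49% (13 scores, uncorrelated), against the 5% that one pre-named test would carry. The loss of power from reading the main effect instead of the interaction depends on the assumed pre-post correlation, but it is large across the whole range tried.

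That 72 matches only a one-sided test is a separate weakness in the sizing. It is already in the plan, and this conclusion does not depend on it.

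**What to change.** Before unblinding, amend Section 6 as follows.

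- **Primary outcome.** Name one that matches the sizing. It may be one cognitive score, with the reason why d=0.60 for a global measure applies to it. Or it may be a defined global composite, for example the mean of baseline-standardised z-scores signed so that higher is better. List the components, including whether finger tapping and both RAVLT entries count.
- **Deciding test.** Test it once, two-sided at 0.05, on the baseline-adjusted between-group difference at 12 weeks, whether or not the arms differ at baseline.
- **Composite rules.** Section 6 says that "extreme outliers will be identified and excluded using boxplots (using 3*IQR rule") and that "subjects with missing data will be excluded from analysis". State what happens when a single component is missing or excluded. For N-back, Section 5 says "This task will be performed while also taking EEG measurements", and EEG is limited to 20 per group. If only that subset performs N-back, leave it out of the composite, because complete-case exclusion would cut the analysis to about 40 people.
- **Efficacy claims.** Base them only on between-group terms and report within-arm changes descriptively.
- **Other outcomes.** Apply Holm, or label them exploratory.
- **Power.** Restate it, with sidedness, for the deciding test.

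The cost is SAP wording, plus one derived variable if a composite is chosen. Power for the deciding test at d=0.60, two-sided 0.05, with adjusted effect d/√(1−r²) and r again assumed:

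| Per arm | Unadjusted | r=0.5 | r=0.7 |
|---|---|---|---|
| 36 | 71% | 83% | 94% |
| 32 (if exclusions leave this many) | 66% | 78% | 91% |

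The downside falls on individual secondary tasks. At the first Holm step over 13 outcomes (0.05/13 = 0.0038), power at d=0.60 and 36 per arm is 34% unadjusted, and 48% or 71% with baseline adjustment at r=0.5 or 0.7.
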